#### b.2. Protections Against Risk

The Principal Investigator will be notified of any adverse events. Participants will receive a follow-up telephone call to assure that the reaction has resolved. If the reaction persists, a referral will be made to the participant’s primary care provider for further evaluation. In situations where there is initial severe distress or when the distress has not been resolved, if suicidal thoughts are present, we will immediately call 911 for further help and stay with the participant until help arrives. **If suicidal ideation or intent is identified, the study team member will follow the study’s suicide protocol. The suicide protocol will utilize an adapted version of the Columbia Suicide Severity Rating Scale to assess mild, moderate or severe risk. If risk is mild study team will notify PI, provide mental health resource guide, advice to speak to their healthcare provider. If the risk is moderate, it will be the same as mild with expression of high concern and strong recommendation to seek care. If the risk is severe, the study team member will call 911 or suicide crisis number or escort to emergency room and immediately notify the PI. We will consult with [name] on referrals and next steps for any all mild and moderate risk patients.** Furthermore, if any physical problems emerge during any of the visits, immediate medical attention will be sought for the participant.

If participants experience any physical problems during any portion of the study, immediate medical attention will be sought for the participant. See the table below regarding alert and actions to be taken.

**Table 4**

Alert	Action Taken
Medical Emergency: 
 
• Chest pains
 
• Excessive bleeding
 
• Fall and cannot get up
 
• Difficulty breathing
 
	If a member of the research team encounters any of these symptoms over the phone, the participant is put on hold and the PI will call 911 immediately. If the situation occurs within the home or during focus groups, the PI and/or research personnel will call 911 immediately and stay with the participant until help arrives.  If participants engage in physical activity virtually, the nurse will assess every five minutes for shortness of breath or any pain at all. If participants verbalize this or shortness of breath is observed the nurses will ask

	
participants to stop any physical activity.
 
Evidence of abuse is follows:
 
 
• Participant states to the PI/research staff that abuse occurs.
 
• The RN observes physical evidence (e.g. black eye, black and blue marks arms/legs).
 
 
The investigators will contact participants and strongly encourage him/her to contact his/her primary care provider and/or Adult Protective Services (phone number will be provided). Based on the situation, the PI may notify Adult Protective Services. The PI will complete an alert form. Note- The possibility of informing an agency about an abusive situation will be stated in the informed consent.

Extreme Home Hazards
 
 
• Exposed electrical
 
• External door missing or cannot be locked
 
• Ceiling, floors caved in
 
• No temperature regulation (e.g. no air or heat- must be extreme)
 
• Major infestation
 
	
The investigators will refer participants to Baltimore City 311 who can refer participants to possible resources for home repairs and/or infestations.

All personnel involved in the study have been fully trained and certified in the protection of human subjects. This certification will be kept current throughout the study. Education in protection of human research participants: The investigators have completed the Johns Hopkins University School of Medicine Research Compliance course. All research personnel on the proposed study will complete the Johns Hopkins University (JHU) School of Medicine Research Compliance Course. The JHU course consists of the University of Minnesota Web modules on Informed Consent, the Consent Process, After Informed Consent, JHU School of Medicine module on local IRB requirements, and achievement of a passing score on the JHU Knowledge Assessment module. According to the policies of the JHU, approval for this research will be obtained from the JHU IRB office for research using human subjects. Participants will be assigned a code number on initial entry and only the code number will identify all subsequent questionnaires. Information needed for follow-up contact (names and addresses) will be kept separately from all other data.

Legal Risks such as the risks that would be associated with a breach of confidentiality:

The risk of breaching study participant confidentiality will be minimized by identifying all participants by code numbers and by securing all data collected in locked files in the PI's office and screening information at the senior center in areas with limited staff access. Pre-coded data collection instruments are prepared for use with study participants at each testing occasion. Identification numbers to assure subject confidentiality will be used. Only one master log of subject names, addresses, telephone number, and study identification assignment will be maintained on site in the locked PI's office. This log, in both hard copy and disk, will be stored in a locked filing cabinet separate from other identifying information. All completed data collection instruments are stored in locked filing cabinets.

Financial risks to the participants: There are no anticipated financial risks to the participants.

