### Approach

**4.a Theoretical Framework:** Self-regulation theory is the theoretical framework for this study. Self-regulation theory involves two tenets: 1) participants manage their response based on their experiences (experiences with pain, depression, and frailty treatments) and knowledge of an event and 2) participants' goals are to maintain comfort and decrease the negative effects of an illness (pain depression and/or frailty) on their lives. The intervention is participant centered and participant driven. This means that the participants' experiences and existing knowledge about pain, depressive symptoms, and frailty will drive the goals that they set. For example, a participant may have experienced pain, depression symptoms, and frailty; she is no longer able to go work in her garden. Her goal may be to be able to garden again. This would provide comfort, decrease the effects of these three conditions, and potentially improve her symptoms.

**Design overview of the study:** The design of the study is outlined in the above figure. The outcomes will determine effect sizes on the intervention's effect on pain and depressive symptoms. Outcomes will be measured at 12 weeks (compare intervention and wait list control group) and at 24 weeks (look at outcomes for wait list control group and outcomes over time for intervention group). Goal attainment will be measured at 12 weeks and 24 weeks. At 24 weeks, we will also conduct virtual semi-structured one on one individual interviews with participants to determine feasibility and acceptability.

The intervention group (n=30) will start the study and will receive eight nurse visits that will be focused on decreasing pain, depressive symptoms, and meeting participant selected goals set in these areas. The wait list control group will receive monthly calls by a study team member to ensure their contact information

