Recruitment will also be conducted via mass marketing. A study team member will identify organizations (e.g. churches, senior high rises) that have established partnerships with the Johns Hopkins School of Nursing Center of Innovative Care in Aging, the Johns Hopkins Center for Health and Aging, and the Johns Hopkins Geriatric Services Frailty registry. The study team will provide each site (Maryland AARP, senior high rises, African American hair salons, etc.) director with flyers. We will send the flyers via email to distribute on social media sites or distribute to mailing lists. We will send messages through Johns Hopkins MyChart for recruiting to patients who have demographics that match the study inclusion criteria. We will not send recruitment messages to individuals who have opted out of receiving them. We will also provide flyers to health care providers of older adults and/or chronic pain patients. We will also use "Word of Mouth" campaigns – volunteers & ambassadors, clinics, and personal contacts. The potential participants will be instructed to contact the research team if they are interested in participating in the research study. A study team member will screen the potential participant and explain the study over the phone. If the individual is eligible a study team member will arrange a video visit to re-screen, explain the study again, ask the participant understanding of the study, and give them an opportunity to ask questions. If the potential subject wishes to participate, the study team member will obtain consent either

by delivering the consents as a hard copy or via DocuSign and conduct the baseline questionnaire. If participants do not do a Docusign consent we will use the following process:

- After the consent designee and participant or LAR review the consent form, the participant or LAR is offered the opportunity to ask any questions and have those questions answered.
- The participant (or LAR) will sign and date/time the paper copy of the informed consent document.
- The consent designee must verify the participant or LAR physically signed the consent document either by viewing via video conference, obtaining a photo of the complete signed consent document; or obtaining verbal confirmation from the participant that she signed the consent form or agreed to participate electronically.
- The signed document is then mailed, emailed, photo/scanned to text or faxed to the consent designee.

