## Visits

**Data Collection Visit One:** The data collector will call or do video visit with patient in order to re-screen for criteria to be in the study. If participant meets criteria, the data collector will have participant sign a consent form.

We will be using DocuSign, the Institution's approved and 21 CFR Part 11-compliant software, to obtain a secure electronic signature. Once the IRB approves our consent form(s), we will use the IRB-approved consent form(s) as the base for the DocuSign template. The IRB-approved document will not be altered other than to overlay locations where signatures, initials, dates or other DocuSign fields will be added to create the study-specific DocuSign template.

We will send the consent to the participant via DocuSign, providing a participant-specific code in advance of sending the document via DocuSign, that will be required when the participant accesses and signs the consent. The consent discussion may take place via phone or video conference (e.g. Zoom). Participants will be given adequate time to consider the research study and ask questions prior to signing the consent form. When ready to sign, the participant will enter their code, verifying that the person signing the consent is the person that we spoke with previously, and sign the consent within the DocuSign system.

(Note: For studies requiring multiple signatures, e.g. two parental signatures or if a witness is required, all individuals will receive codes in order to sign). Once the participant has electronically signed, the study team member obtaining informed consent will be notified that the electronic form is ready for his or her signature. Once signing is completed by all parties, both the study team and the participant can download the signed consent as a PDF. The study team will also have access to the audit log and the Certificate of Completion. The study team will load the signed consent into Epic.

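### Table 4's phone rule puts a participant in a medical emergency on hold while the PI calls 911; the team member on the contact should call and stay connected

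*Combined protocol and SAP*

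**What the plan says.** Table 4 (section 6, Risks) has a Medical Emergency row with four triggers: chest pains, excessive bleeding, a fall from which the person cannot get up, and difficulty breathing. If any research team member meets one of these over the phone, the action is that "the participant is put on hold and the PI will call 911 immediately".

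The next sentence of the row covers emergencies within the home or in focus groups. There, "the PI and/or research personnel will call 911 immediately and stay with the participant until help arrives".

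The row then turns to remote exercise: "If participants engage in physical activity virtually, the nurse will assess every five minutes for shortness of breath or any pain at all". If either is reported, or breathlessness is seen, the nurse asks the participant to stop.

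Section b.2, Protections Against Risk, promises immediate medical attention for physical problems and then points to Table 4: "See the table below regarding alert and actions to be taken". In the same section, when suicide risk is severe, "the study team member will call 911 or suicide crisis number or escort to emergency room and immediately notify the PI".

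**The concern.** The phone sentence is triggered by any team member but names only the PI as caller. Read literally, a nurse or data collector who hears a participant struggling to breathe puts her on hold, finds the PI, and the PI dials. The participant meanwhile has no voice on the line, and the person placing the call is not the one who heard the symptoms.

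The population makes this worth tidying. Participants must be pre-frail or frail (Inclusion/Exclusion Criteria). The Medical risks subsection expects minimal risk overall, but lists falls, shortness of breath and dizziness as possible. The Adverse Event Reporting text foresees that staff may meet a medical emergency during remote contact and relies on the alert procedures to deal with it. At stake is how quickly and safely such an event is handled. No estimate or test depends on it.

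**Working it through.** No arithmetic applies. The check sets the protocol's emergency rules side by side and then asks who is likely to be on the phone.

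**Step 1: the rules compared.**

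| Situation | Who calls | Contact with the participant |
|---|---|---|
| Medical emergency by phone (Table 4) | The PI; no alternative named | On hold |
| Medical emergency in the home or a focus group (Table 4) | PI and/or research personnel | Caller stays |
| Severe suicide risk (b.2) | The study team member, who also notifies the PI at once | Not stated in that sentence, apart from the option to escort |
| Symptoms during virtual exercise (Table 4) | No call mentioned in that sentence | Nurse checks and stops the activity |
| Physical problems in general (b.2, and Steps taken to minimize the risks) | No caller named | Not stated |

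The phone rule is the only one that reserves the call to the PI and the only one that interrupts contact. The general promise does not repair it: it names no caller, does not require contact to be kept, and in b.2 sends the reader to the table that holds the phone rule.

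**Step 2: who is on the phone.**

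- Approach, design overview, on keeping contact details current: "The wait list control group will receive monthly calls by a study team member to ensure their contact information".
- Recruitment text under Inclusion/Exclusion Criteria: "A study team member will screen the potential participant and explain the study over the phone".
- Data Collectors and Research Nurses paragraphs: each role telephones participants to schedule its first contact.
- Visits section, in its opening entry on the baseline contact: "The data collector will call or do video visit with patient in order to re-screen for criteria to be in the study".
- Nurse Visit One: the participant may ring the nurse or the PI about difficulties with a strategy.
- Acceptability Qualitative Interviews: a study team member conducts interviews by phone or video. The closing text of that section adds calls to those who completed the intervention.

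Nurses and data collectors are named for several of these. A study team member could be the PI, so the list shows that staff other than the PI make many phone contacts. It does not show how often the PI is absent.

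**Step 3: what the rule does.**

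- PI on the line: there is no relay.
- PI not on the line: hold, reach the PI, pass on the details, PI dials. If the team member placed the call, the middle two steps would not come before it, and with a second line the hold would not be needed.

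**Step 4: size.** The documents give no emergency rate, no response time and no split of contacts by mode or by caller. No delay or number of affected participants can be derived.

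**The case against.** The strongest case on the other side has five parts.

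*Different settings may have different rules.* A reader might infer that the phone rule contradicts the in-home and suicide-risk rules. The documents do not support that. Table 4 gives separate instructions for separate settings, and the suicide protocol covers a different event with its own assessment scale. What stands is that the phone rule is less direct than its neighbours.

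*The delay is conditional.* The sentence says the call is immediate, and a hold is not a disconnection. This is fair. The relay arises only when someone other than the PI is on the line, and nothing shows that harm would follow.

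*There may be a reason to route the call through the PI.* The confidentiality text after Table 4 keeps the master log of names and addresses in the PI's locked office, and contact details are held apart from other data. It is a plausible inference, though not one the protocol states, that the PI can best reach the address. Asking the participant where she is answers this without changing the storage rules.

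*Video may already be covered.* A reader might infer that Zoom emergencies have no 911 rule. That goes too far. A participant on Zoom at home can be read as within the home, and the exercise sentence can be read as a precaution on top of the row's 911 instruction. Staying with the participant can also be read as in person, so the wording is ambiguous, but it is not a demonstrated gap.

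*Risk is minimal and staff are trained.* The protocol expects minimal risk and says the nurses can recognise respiratory distress over Zoom. That limits how much weight the point deserves. It does not settle who dials.

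**Conclusion.** The point holds as a cheap improvement to participant safety. For a phone emergency, Table 4's literal wording adds a relay before the 911 call and breaks contact whenever the PI is not on the line, and no other text in the protocol corrects this.

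The conclusion rests on two things: that staff follow the sentence as written, and that people other than the PI make some of the phone contacts. The named roles support the second. It would be tempting to count phone contacts as a measure of risk. Such a count would show only exposure to the rule, would depend on an uncertain length of wait for the control group, and would say nothing about how many emergencies to expect. The harm therefore stays unsized. No endpoint, estimate, sample size or analysis is affected.

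**What to change.** Replace the phone sentence in Table 4 with:

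> If symptoms are encountered by phone or video, the research team member on the contact calls 911 immediately on a second line, gives the participant's location, stays connected until help arrives, and then notifies the PI.

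Keep the present in-home sentence for in-person visits. Naming video in the new sentence removes the ambiguity about Zoom; it is a clarification, not the correction of an error.

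Ask the participant for her current location at the start of every remote contact. Participants may be in Maryland, Virginia or the Washington DC area, so the caller needs it to hand. Asking on the day also means that the separate storage of names and addresses, and the master log arrangements, need not change.

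The cost is a wording amendment, a short staff briefing, one extra question per remote contact and access to a second line. There are no additional visits or outcome data.

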has not changed. Data collection, nurse visits, and interviews will be completed via Zoom video calls. Zoom is a HIPAA compliant virtual meeting software used for telehealth purposes. The study will include either in person or virtual visits depending on the preference of the participants. The study team completing in person visits have all been fully vaccinated and will wear personal protective equipment at visits. In addition, study team will screen all research participants for symptoms of COVID based on the Johns Hopkins University of Medicine including fever, cough, sore throat, shortness of breath, acute loss of taste or smell, headache, vomiting or nausea, new fatigue or runny nose in the last 72 hours. The study team will reschedule if participants exhibit any of these symptoms at a later date when participants are symptom free for 72 hours or have a negative Covid-19 test.

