## **DAPPER Protocol**

### **Inclusion/Exclusion Criteria**

Inclusion criteria: 1) self-reported pain  $\geq 3$  out of a 0 -10 scale that has lasted longer than 3 months and keeps them from doing at least one activity that they would like, 2) Self-Identify as African American/Black female 3) non-institutionalized and living in the community Maryland, Virginia or Washington DC area. 4) score a 5 or higher on the PHQ9 (depression measure) at least two times during a two week period (screening call and then at first data collection visit via video), 5) pre-frail ( one or two criteria on frailty phenotype) or frail (three or more of the criteria on frailty phenotype), 6) at least one ADL or IADL limitation Exclusion Criteria: 1) Hospitalized  $> 3$  times in the last year, 2) participating in physical therapy, 3) have a terminal diagnosis ( $< 1$  year expected survival), 4)  $\geq$  moderate intellectual impairment (5-7 errors) based on the Short Portable Mental Status Questionnaire (SPMSQ), 5) Unable to understand or speak English

We will recruit participants from the PI's Communication Behaviors and Development of Pain and Depression Intervention among Older African American Women (IRB000170533) study. This study consisted of focus groups for the development of the DAPPER intervention. We will only contact participants who agreed to be contacted for future studies. We will contact these participants by phone and ask them if they are interested in participating in the intervention (please see the phone script). If participants agree to this, we will screen them on the phone at this time.

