After the informed consent process is completed, the IRB approved study team member files the consent document in the research record, including a note confirming the consent process. The data collector will verify if the participant has any questions regarding the consent form and verify the participant understands the consent form. The data collector will ensure that the participant reads the consent form and has a copy of the consent form. After the consent is completed, a formal assessment of outcomes will be done. The data collector will explain the process of saliva sample collection to the participant. We will not collect saliva samples from participants outside of Maryland. A kit will be dropped off to the participants with non-contact either at their door or given to front office. We will call and confirm participants receive the kits. The participants will be asked to store samples in their home refrigerator. If there is not a working refrigerator, the participants will be provided with a cooler and ice packs that will be replaced over the two days. When the participant is ready for the saliva sample to be picked up, they will notify us, and it will be picked up using protective gear (gown, gloves, and mask) without contact with participants and stored in the Johns Hopkins School of Nursing lab.

**Final Data Collection Visit:** At this visit, the data collector will enact the same protocol as at baseline.

**Saliva Sample Visits:** A member of the research staff will contact the participants to ask them a good time to pick up samples. The research staff member will arrive to participants home to pick up samples. Personnel picking up the samples will notify participants when they are arriving, and participants will place the sample outside the front door once the staff member pulls up or walks up to their home location. The staff member will label the specimens and take them directly to the Johns Hopkins School of Nursing refrigerator. Please see specifics below (laboratory studies) for further information about the collection and storage process of the saliva samples.

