### b. Steps taken to minimize the risks.

Participants can decline the saliva specimen collection or stop collecting specimens at any time. Participants can decline saliva collection or stop at any time. Participants can also decline to answer any of the survey questions. Research staff has been trained to interact with participants in a positive, non-judgmental manner that encourages honest communication and a partnership approach to study participation. Participants may decline the walking speed test, or any exercise strategies suggested by the nurse. The nurses have the necessary training to recognize respiratory distress and how to reduce falls (e.g. removal of clutter, assessing for dizziness and balance) via Zoom. The principal investigator will be made aware of any adverse reactions or events. Participants will receive a follow-up telephone call to assure that the reaction/event has resolved. If the reaction/event persists, a referral will be made to the participant's primary care provider for further evaluation.

Procedures for protecting against and minimizing potential risks:

If any physical problems emerge during any of the home visits, immediate medical attention will be sought for the participant. The risk of invasion of privacy will be addressed with participants during the informed consent process. All personnel involved in the study will be fully trained and certified in the protection of human subjects and HIPAA regulations. We will use a virtual video call software called Zoom. Zoom is encrypted, collects no protected health information (PHI) and any data transmitted during the call is destroyed when the call ends. It is both HIPAA and HITECH compliant.

This certification will be kept current throughout the study. As part of the informed consent process, participants will be notified of their rights pertaining to protected health information. Participants will be informed that they can stop the questionnaire and rest at any time. All study participants will be provided referral information to existing health services as in typical or usual care. Thus, participants have the information to access any services that they may perceive as necessary independent of their study participation.

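### Table 4 refers every extreme home hazard to Baltimore City 311, although women elsewhere in Maryland, in Virginia or in the Washington DC area are eligible

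*Combined protocol and SAP*

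**What the plan says.** Table 4 in Section 6 (Risks) pairs alert events with the action staff should take. The Extreme Home Hazards row covers five situations: exposed electrical hazards, an external door that is missing or will not lock, collapsed ceilings or floors, an extreme lack of heating or cooling, and major infestation. One action serves all five: "The investigators will refer participants to Baltimore City 311 who can refer participants to possible resources for home repairs and/or infestations". The row names no other service and makes no allowance for a local equivalent.

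Inclusion criterion 3, under DAPPER Protocol, Inclusion/Exclusion Criteria, requires that a participant be "non-institutionalized and living in the community Maryland, Virginia or Washington DC area". Under Visits, Data Collection Visit One, the saliva procedure makes an exception for the wider area: "We will not collect saliva samples from participants outside of Maryland".

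The nearest general referral provision is in Section 6, part b: "All study participants will be provided referral information to existing health services as in typical or usual care".

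**The concern.** The eligible area is much wider than the city named in the hazard row. The saliva procedure makes allowance for women outside Maryland; this row does not.

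Staff who follow the row as written would give a woman in Virginia, in the Washington DC area, or elsewhere in Maryland a contact that does not match where she lives. The hazards listed are serious ones, such as exposed wiring or a home without heat. Participants must be pre-frail or frail and have at least one ADL or IADL limitation, so finding the right local service unaided may be harder for them than for most people. What is at stake is a safety instruction that should be right for every eligible participant. The statistical design is not affected.

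**Working it through.** The protocol gives no figure to reproduce here. The check compares sections and then bounds the number affected.

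**1. Who can be enrolled.** Criterion 3 covers Maryland, Virginia and the Washington DC area, and does not restrict enrolment to Baltimore City.

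**2. Whether enrolment outside Maryland is really expected.** It is. A rule against collecting saliva outside Maryland would be unnecessary if no such participants were foreseen.

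**3. Whether staff could notice a hazard in those homes.** They could. On format, the design overview under Approach states: "The study will include either in person or virtual visits depending on the preference of the participants". Under Visits, the nurse watches the participant carry out her strategies at visits four and five, with exercises in the home given as an example. The wait-list group later receives the same visits, so the row can apply in either arm.

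**4. What staff are then told to do.** They are to refer to Baltimore City 311 in every case. That this line serves one city is read from its name; the documents do not describe its coverage.

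**5. Whether another section fills the gap.** I found none that does.

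| Place in the protocol | What it covers | A home-hazard route outside Baltimore City? |
|---|---|---|
| Section 6b, general referral statement | Referral information for health services | No |
| Section 6, Adverse Event (AE) Reporting and the alert text after it | Counts environmental risk among alerts, says management procedures exist, points to the chart | No; it leads back to Table 4 |
| Section 6, b.2 Protections Against Risk | Distress, suicide risk, physical problems; then points to Table 4 | No |
| Table 4, medical emergency and abuse actions | 911 and Adult Protective Services, with no city named | Not relevant; these actions are not questioned |

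**6. Size.** Let *p* be the share of participants living outside Baltimore City and *h* the share of those with an extreme hazard that staff notice. The planned sample in Section 5 is 64, so

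number affected = 64 × *p* × *h*.

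Neither share is in the documents. If either is 0, the result is 64 × 0 = 0. If both are 1, it is 64 × 1 × 1 = 64. Only these bounds can be stated. The upper one is a formal limit, not an expectation.

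**The case against.** The textual mismatch is hard to dispute, so the case against concerns its consequence and weight.

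- **The service area is inferred.** The row presents 311 as a contact that passes people on to other resources, and it might redirect a caller from elsewhere. This stands as a limit on what can be said about harm. The documents do not say that it would redirect anyone, and a written safety action should not depend on it.
- **The general referral text is broader than one sentence.** The sentence after the one quoted from Section 6b says participants can reach whatever services they feel they need. It is drawn as a consequence of the health-service information, however, so it supplies no housing referral.
- **There is other oversight.** Alerts are reported to the DSMB twice a year, and nothing forbids an investigator from naming a local service. Both points are true. But periodic reporting does not give a participant the right contact when the hazard is seen, and staff discretion is no substitute for a correct instruction.
- **Few women, perhaps none, would be affected, and the science is untouched.** This stands in full and is why the point ranks low.
- **The master log may be awkward to consult.** The Legal Risks text keeps it in a locked office. This is a fair practical remark: staff can simply ask the participant where she lives.

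**Conclusion.** The concern holds. The only action given for extreme home hazards names one city's line, while eligibility extends across Maryland, Virginia and the Washington DC area, and no other section supplies a route for women elsewhere.

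Confidence in the mismatch is high, because both statements are complete, current text. The practical consequence rests on one assumption: that Baltimore City 311 is, as its name suggests, a service for that city. The number of women affected is unknown, somewhere from 0 to 64, and quite possibly 0.

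This is a small safety correction for the sponsor to consider, confined to this one row. No estimate, comparison or conclusion of the trial depends on it.

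**What to change.** In the Extreme Home Hazards row of Table 4, replace the reference to Baltimore City 311 with: the 311 or equivalent housing or home-hazard service for the participant's place of residence. Attach a short referral list covering the area in criterion 3.

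Staff can choose the entry by asking the participant where she lives or from the address already on file. On the latter, the Legal Risks text says: "Only one master log of subject names, addresses, telephone number, and study identification assignment will be maintained on site".

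The cost is one reworded table cell and the list. No extra staff, visits or data collection are needed.

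A separate, optional safeguard would be to confirm the participant's current location and call-back number at the start of each remote contact, so that anyone calling 911 has them to hand. It is not part of this repair.
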